3.1. Study Rationale

A prandial insulin with faster-onset and/or faster-offset characteristics might reduce glycemic excursions and decrease the incidence of delayed postprandial hypoglycemia compared to currently available rapid-acting insulin analogs. The insulin analog, insulin lispro (Humalog®), has been shown to be absorbed more quickly than regular human insulin (Humalog package insert, 2015). In healthy volunteers given subcutaneous (SC) doses of insulin lispro ranging from 0.1 to 0.4 U/kg, peak serum levels were seen 30 to 90 minutes after dosing. Rapid-acting insulins have been shown to have a more rapid onset of action compared to human insulin; however, the general consensus is that they are not rapid enough to match carbohydrate absorption and many patients are unable to achieve optimal glycemic control. An ultra-rapid-acting prandial insulin with pharmacokinetic (PK) and glucodynamic (GD) profiles that demonstrate faster absorption and onset of action, may better match carbohydrate absorption and lead to improved postprandial control. The time action profile of a rapid-acting insulin could be enhanced through the addition of excipients to an existing formulation to increase capillary blood flow and/or enhance vascular permeability. An ultra-rapid insulin (URI) would be useful in the treatment of type 1 diabetes (T1D) and type 2 diabetes (T2D) when delivered by multiple daily injections (MDI), by continuous subcutaneous insulin infusion (CSII), and in the development of closed loop insulin delivery systems.

The aim of this study is to demonstrate that an ultra-rapid formulation of insulin lispro, LY900014, is noninferior to insulin lispro on glycemic control as measured by change from baseline to Week 26 in hemoglobin A1c (HbA1c) in patients with T2D when administered in a double-blind manner as prandial insulin in combination with basal insulin glargine or degludec in accordance with local regulations. The study will expand the evaluation of the efficacy and safety of LY900014 to a broader race/ethnic spectrum of patients with T2D.

3.2. Background

Type 2 diabetes can remain asymptomatic for many years, and about 50% of people with T2D are undiagnosed (IDF [WWW]). The global prevalence of diabetes in 2015 among adults was estimated to be 9.0% or 415 million people, with greater than 90% of these cases being T2D (IDF [WWW]).

There have been many advances in the treatment of T2D in the last 20 years; however, reaching and maintaining glycemic goals remains challenging even under intensive insulin therapy regimens. Although estimates on the number of patients with diabetes not meeting targets vary, the values are consistently high. An analysis of NHANES data from 2007-2010 found that almost half of US adults with diabetes do not meet the HbA1c target of $\leq 7.0\%$ (Ali et al. 2013). Another analysis of NHANES data showed that after improvements in glycemic control between 1999 and 2006, the HbA1c level plateaued through 2014 and the proportion of patients achieving HbA1c $< 7\%$ has remained relatively unchanged between the two most recent waves of data (Carls et al. 2017). The UK National Diabetes Audit 2015–2016 reported that HbA1c levels were $> 7.5\%$ in more than two thirds (70.8%) of people with T1D and in more than one third

(34.3%) of those with T2D (NHS 2017) Currently available rapid-acting insulin analogs are unable to match the kinetics of physiological postmeal insulin secretion, which is biphasic. Normal first-phase insulin response is a rapid but short-lived increase in secretion, which is then followed by a more slowly developing prolonged increase (Barrett et al. 2016). First phase insulin release prevents the rapid development of postprandial hyperglycemia, while second phase release of insulin ensures that glucose enters tissues in a steady, controlled manner throughout the late postprandial period. Thus, there remains a need to continue to develop formulations with a time action profile that more closely approximates that of endogenous insulin secretion.

Insulin lispro is indicated to be administered within 15 minutes before a meal or immediately after a meal (Humalog package insert, 2015). Ideally, currently available rapid-acting insulin analogs should be injected 10 to 15 minutes prior to meal consumption in order to control postprandial glucose (PPG). However, many people inject their rapid-acting insulin at the time of the meal or after the meal. According to survey data from the T1D Exchange on the timing of prandial insulin injection, 21% of patients reported administering insulin several

minutes before meals, 44% immediately before meals, 10% during meals, and 24% after meals (Dayte et al. 2017).. Because patients often inject later than recommended, there is a greater mismatch between insulin action and postprandial blood glucose (BG) elevations. With postmeal dosing, the mismatch between the rise in BG and the onset of insulin action is even more pronounced. For the development of a URI, it will be important to understand the relationship between time action profile of the insulin, insulin injection timing, and meal timing in order to maximize improvements in postprandial glycemic control and minimize hypoglycemia risk. A URI with higher early insulin concentration and peak exposure, and shorter duration should improve early postprandial control and limit postmeal hyperglycemia, while reducing late postprandial hypoglycemia due to lower insulin exposure. Patients will administer Humalog at 0 to 2 minutes before the start of the meal to maintain the study blind.

Hemoglobin A1c provides an integrated measurement of both fasting and postprandial glycemic control and is the most reliable marker for overall glucose exposure. Elevation in HbA1c is the best predictor of diabetes complications. Control of both fasting and postprandial hyperglycemia is essential to reach HbA1c goals. The relative contribution of postprandial hyperglycemia is predominant with moderate to fairly well controlled HbA1c levels (Monnier et al. 2003).

A new pharmaceutical innovation that may allow more effective control of PPG levels is LY900014, a new formulation of insulin lispro developed as an ultra-rapid acting insulin with a faster onset of action and shorter duration of action compared to currently available rapid-acting insulin analogs. The changes in PK and GD characteristics are achieved by coformulating insulin lispro with treprostinil and ingredients Generally Recognized As Safe (GRAS) by the US Food and Drug Administration (FDA) as excipients.

LY900014 is a formulation of insulin lispro that contains the prostacyclin analog treprostinil, citrate, and other excipients. Treprostinil as an excipient enhances the absorption of insulin lispro by local vasodilatation rather than as an active pharmaceutical ingredient that elicits a

systemic effect. Treprostinil is a prostacyclin analog administered either by inhalation (Tyvaso®), intravenous (IV) infusion, or continuous subcutaneous infusion (Remodulin®) for the treatment of symptomatic pulmonary arterial hypertension, and has been approved in the United States since 2002 (Remodulin package insert, 2014) and in Europe since 2005 (PMR [WWW]). Sodium citrate, an excipient that speeds insulin absorption, is also included in the formulation to further enhance the absorption of insulin lispro. Sodium citrate and the other excipients in the LY900014 formulation are listed in the FDA GRAS food additives database and in the FDA Inactive Ingredients in Approved Drugs database. Furthermore, the excipient concentration in LY900014 is within the limits identified for approved drug products in the FDA Inactive Ingredients in Approved Drugs database.

Refer to the Humalog local product labeling (for example, Humalog package insert, 2015; Humalog Summary of Product Characteristics, 2016) for more information regarding insulin lispro.

The Investigator's Brochure (IB) describes the clinical and nonclinical development of LY900014.

3.3. Benefit/Risk Assessment

More detailed information about the known and expected benefits and risks of insulin lispro may be found in the country-specific product labeling (for example, Patient Information Leaflet, Package Insert, or Summary of Product Characteristics).

Across all doses in the Eli Lilly and Company (Lilly) clinical studies that have evaluated treprostinil as a local vasodilator with or without insulin lispro, there was no clinically significant increase in those adverse events (AEs) associated with systemic absorption of treprostinil, as described in the Remodulin package insert (2014) (that is, headache, diarrhea, nausea, jaw pain, vasodilatation, rash, edema, anorexia, vomiting, asthenia, abdominal pain, and hypotension). The exposures of treprostinil in LY900014 for participants in upcoming and future clinical trials are expected to be much lower than those observed in the dose ranges previously explored with SC bolus administration of treprostinil and are expected to be substantially lower than those observed in the treatment of pulmonary artery hypertension. Treprostinil is unmeasurable in the serum after administration of LY900014 in doses expected to be used in the clinical setting.

More information about the known and expected benefits, risks, serious adverse events (SAEs) and reasonably anticipated AEs of LY900014 can be found in the IB.

4. Objectives and Endpoints

Table ITSE.1 shows the objectives and endpoints of the study.

Table ITSE.1. Objectives and Endpoints

Objectives	Endpoints
Primary Objective	

 To test the hypothesis that LY900014 is noninferior to insulin lispro on glycemic control (NIM=0.4% for HbA1c) in patients with T2D, when administered as prandial insulin (0 to 2 minutes prior to the meal), in combination with basal insulin glargine or insulin degludec for 26 weeks 	
 Difference between LY900014 and insulin lispro in change from baseline to Week 26 in HbA1c
Multiplicity-Adjusted Objectives	

 To test the hypothesis that LY900014 is superior to insulin lispro in controlling 1-hour PPG excursions, when administered as prandial insulin 	
 Difference between LY900014 and insulin lispro in the 1-hour PPG excursion (serum glucose measured 1 hour after the start of the meal minus fasting serum glucose) from an MMTT at Week 26

 To test the hypothesis that LY900014 is superior to insulin lispro in controlling 2-hour PPG excursions when administered as prandial insulin 	
 Difference between LY900014 and insulin lispro in the 2-hour PPG excursion (serum glucose measured 2 hours after the start of the meal minus fasting serum glucose) from an MMTT at Week 26

 To test the hypothesis that LY900014 is superior to insulin lispro on improving glycemic control (HbA1c) when administered as prandial insulin 	
 Difference between LY900014 and insulin lispro in change from baseline to Week 26 in HbA1c
Other Secondary Objectives	

 To compare LY900014 and insulin lispro with respect to the rate of severe hypoglycemic events 	
 Rate (events/patient/100 years) of severe hypoglycemic events from baseline through Week 26

 To compare LY900014 and insulin lispro with respect to the incidence and rate of documented symptomatic postmeal hypoglycemia 	
 Rate (events/patient/year and/or events/patient/30 days) and incidence (percent of patients with at least 1 event) of documented symptomatic postmeal hypoglycemia within 1 and 2 hours after start of a meal from baseline through Week 26

 To compare LY900014 and insulin lispro with respect to the incidence and rate of documented symptomatic hypoglycemia 	
 Rate (events/patient/year and/or events/patient/30 days) and incidence (percent of patients with at least 1 event) of documented symptomatic hypoglycemic events from baseline through Week 26

 To compare LY900014 and insulin lispro with respect to 1,5-AG 	
 Change from baseline in 1,5-AG values at Week 26

 To compare LY900014 and insulin lispro with respect to 10-point SMBG profiles 	
 Change from baseline in 10-point SMBG values at Week 26

 To compare LY900014 and insulin lispro with respect to total, basal, and prandial insulin dose 	
 Change from baseline in total, basal and prandial insulin dose and prandial/total insulin dose ratio at Week 26

Objectives and Endpoints

Objectives	Endpoints
Other Secondary Objectives (Continued)	

 To compare LY900014 and insulin lispro with respect to the proportion of patients achieving HbA1c targets 	
 The proportion of patients with HbA1c <7% and ≤6.5% at Week 26
Tertiary/Exploratory Objectives	

 To compare the safety of LY900014 relative to insulin lispro 	
 Adverse events, vital signs, chemistry, and hematology laboratory measures

 To compare the incidence of treatment-emergent anti-insulin lispro antibodies for LY900014 and insulin lispro 	
 Incidence of treatment-emergent positive anti-insulin lispro antibodies

 To compare LY900014 and insulin lispro with respect to quality of life as measured by the EQ-5D-5L 	
 Change from baseline in EQ-5D-5L UK-population based health state index score and EQ-VAS score at Week 26

 To compare LY900014 and insulin lispro with respect to diabetes treatment satisfaction as measured by the ITSQ 	
 Change from baseline in ITSQ regimen inconvenience and lifestyle flexibility domain scores at Week 26

 To compare LY900014 and insulin lispro with respect to the impact that diabetes has on the ability to work and perform regular activities as measured by the WPAI-GH 	
 Change from baseline in WPAI-GH item scores at Week 26

 To compare LY900014 and insulin lispro with respect to changes in body weight 	
 Change from baseline to Week 26 in weight (kg)

 To compare LY900014 and insulin lispro with respect to glycemic variability 	
 Within-day and between-day glycemic variability measured by the standard deviation and the coefficient of variation of 10-point SMBG profiles

Abbreviations: 1,5-AG = 1,5-Anhydroglucitol; EQ-5D-5L = European Quality of Life – 5 Dimensions 5 Level; EQ-VAS = EuroQol visual analog scale; HbA1c = hemoglobin A1c; ITSQ = Insulin Treatment Satisfaction Questionnaire; MMTT = mixed-meal tolerance test; NIM = non-inferiority margin; PPG = postprandial glucose; SMBG = self-monitored blood glucose; T2D = type 2 diabetes; WPAI-GH = Work Productivity and Activity Impairment Questionnaire General Health.

5. Study Design

5.1. Overall Design

[figure not shown]
Study I8B-FH-ITSE (ITSE) is a Phase 3, prospective, double-blind, randomized, multinational, multicenter, 2-group, parallel, active-controlled study conducted in patients with T2D currently treated with basal insulin in combination with at least 1 prandial insulin injection OR premixed insulin with at least 2 injections daily. Patients will be randomized to 1 of the 2 treatment groups in 2:1 ratio (LY900014: insulin lispro). Each of the treatment therapies, LY900014 and insulin lispro, will be administered immediately (0-2 minutes) prior to each meal in a double-blind manner. The study is designed to demonstrate noninferiority of LY900014 when compared with insulin lispro in change from baseline to Week 26 in HbA1c, when both are administered at the start of the meal. The study includes a 1-week screening period and an 8-week lead-in period, followed by a 26-week treatment period, and a 4-week safety follow-up period.

The purpose of the lead-in period (prior to randomization) will be to titrate basal insulin, obtain preliminary diagnostic laboratory tests, and determine baseline hypoglycemia rates. Patients treated with either a) basal insulin (insulin glargine U-100, insulin degludec U-100, insulin detemir or neutral protamine Hagedorn [NPH] insulin) in combination with at least 1 prandial injection of bolus insulin or b) at least 2 injections of premixed insulin will be eligible for inclusion in the trial.

Patients should use the same study basal insulin regimen throughout the trial, with allowed regimens as follows: insulin glargine U-100 (Basaglar/Abasaglar or LANTUS) once daily or insulin degludec U-100 once daily in accordance with local regulation. Patients using basal insulin regimens other than insulin glargine U-100 or degludec U-100 will be transferred at Visit 2 to an allowed study basal insulin regimen, which will be chosen by the investigator. Basal insulin will be titrated during the 8-week lead-in period using a titration algorithm to allow the patient to reach the target fasting blood glucose (FBG) by the end of this period.

Patients treated with insulin aspart, insulin glulisine, regular human insulin, or premixed insulin will be transferred to insulin lispro at Visit 2, so that all patients will be treated with insulin lispro throughout the lead-in period. Patients treated with 1 to 2 prandial injections a day or premixed insulin prior to study entry will transition to 3 injections a day of prandial insulin lispro at the beginning of the lead-in period. At Visit 8, patients will be randomized to either LY900014 or insulin lispro at each meal. During the initial 12 weeks after randomization (intensive titration period), prandial insulin doses should be titrated as necessary in order to meet the target self-monitored blood glucose (SMBG) levels. Basal insulin may be titrated as needed to facilitate optimal prandial dosing or for safety reasons such as hypoglycemia or unacceptable hyperglycemia. Thereafter, during the maintenance period (Weeks 12-26 of treatment), it is expected that adjustments to prandial and basal insulin doses would be to maintain glycemic control or for safety reasons such as hypoglycemia or unacceptable hyperglycemia.

[Figure ITSE.1](#) illustrates the study design.

Abbreviations: T = telephone visit; wk = week.

- a At Visit 2, patients treated with insulin aspart, insulin glulisine, regular insulin, or premixed insulin will be transferred to insulin lispro. At Visit 2, patients treated with a basal insulin regimen other than insulin glargine U-100 or insulin degludec will be transferred to insulin glargine U-100 once daily or insulin degludec U-100 once daily. At Visit 8, patients will be randomized to either insulin lispro or LY900014 and continue their basal insulin regimen.
- b Titrate basal insulin.
- c Titrate prandial insulin (insulin lispro or LY900014).
- d Patients will discontinue study insulins at Week 26.

Figure ITSE.1. Illustration of study design for Clinical Protocol 18B-FH-ITSE.

5.2. Number of Participants

Approximately 705 patients will be screened to achieve 564 randomized patients and 480 patients completing 26 weeks of treatment. Approximately 450 Chinese patients will be randomized. The other 114 randomized patients are planned to be from other countries, which may include Mexico, Argentina, Brazil, India and Ukraine. The final participating countries and allocated patient numbers will be adjusted based on the actual condition.

5.3. End of Study Definition

End of study is the date of the last visit or last scheduled procedure shown in the Schedule of Activities (Section 2) for the last patient.

5.3.1. Safety Follow-Up Period

Safety follow-up visit guidelines are as follows (see Section 2):

- For patients who discontinue from the study early during the lead-in period (prior to randomization), only an early discontinuation visit should be completed.
- For patients who discontinue from investigational product (IP) early but remain in the study, all remaining visits should be completed per the Schedule of Activities (Section 2).
- For patients who discontinue from the study early (regardless of whether they discontinue IP at the same time or have discontinued IP at an earlier visit), an early discontinuation visit followed by the safety follow-up visit (Visit 801) should be completed as per the Schedule of Activities (Section 2).
- For patients who finish Visit 18 without early discontinuation of IP, a safety follow-up visit should be completed 4 weeks after Visit 18.

5.4. Scientific Rationale for Study Design

Study ITSE is a Phase 3 study to evaluate LY900014 compared to insulin lispro each in combination with basal insulin glargine or degludec in patients with T2D. The trial has 2 double-blind treatment groups, to allow comparison of LY900014 and insulin lispro when injected at the start of the meal. The 2:1 randomization ratio is to meet the regulatory requirement of China SDA.

The study is designed to compare HbA1c lowering as the primary endpoint, a measure of glycemic control accepted by health care providers and regulatory authorities as a validated measure of glycemic control over time and as the best marker for the development and progression of diabetes complications. The lead-in period consists of 8 weeks to allow for optimization of basal insulin dosing. The 26-week treatment period consists of a 12-week intensive titration period to optimize prandial insulin dosing followed by a 14-week maintenance period to ensure that the primary endpoint HbA1c reflects glycemic control on the patient's insulin regimen.

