10.1. Sample Size Determination

Approximately 564 patients will be randomized in order that 480 patients complete the study through the primary endpoint at Week 26.

The primary objective of this study is to test the hypothesis that LY900014 is noninferior to insulin lispro on glycemic control as measured by change from baseline to Week 26 in HbA1c in patients with T2D when administered in a double-blind manner as prandial insulin in combination with basal insulin glargine or insulin degludec and OAM.

Patients will be randomized in a 2:1 ratio to LY900014 and insulin lispro, both dosed 0 to 2 minutes before meals. Assuming a non-inferiority margin (NIM) of 0.4%, no true difference between treatment arms, and an SD of 1.1%, 480 completers (320 in the LY900014 group and 160 in the insulin lispro group) will provide 96% power to show noninferiority between LY900014 and insulin lispro using the upper limit of a 2-sided 95% confidence interval (CI; LY900014 – insulin lispro). Assuming a 15% dropout rate for 26 weeks, approximately 564 patients will need to be randomized.

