### **6.5. Multiple Comparisons/Multiplicity**

A graphical approach for multiple comparisons will be used to strongly control the overall Type I error (2-sided alpha level of 0.05) for testing the treatment effect for the primary and the multiplicity adjusted objectives given in Section 4. See Section [6.11.2](#) for the details of graphical testing scheme.

No multiplicity test adjustment will be made for other objectives.

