## 6.11. Efficacy Analyses

### 6.11.1. Primary Outcome and Methodology

The primary objective of this study (H1) is to test the hypothesis that LY900014 is noninferior to insulin lispro on glycemic control (NIM=0.4% for HbA1c) in patients with T2D, when administered as prandial insulin (0 to 2 minutes prior to the meal), in combination with basal insulin for 26 weeks.

The primary efficacy comparison will be based on the contrast between LY900014 and insulin lispro at Week 26 (Visit 18) from the MMRM analysis of change from baseline in HbA1c including data collected from all randomized patients prior to permanent discontinuation of IP through Week 26. The model for the analysis of the primary efficacy endpoint of change from

baseline in HbA1c will include the fixed class effects of treatment, strata (country, type of basal insulin during the lead-in period, and number of prandial doses at study entry), visit, and treatment-by-visit interaction, as well as the continuous, fixed covariates of baseline value. An unstructured covariance structure will be used to model the within-patient errors. Significance tests will be based on LS means and Type III tests. If this analysis fails to converge, the following covariance structures will be tested in order:

- Toeplitz with heterogeneity
- autoregressive with heterogeneity
- compound symmetry with heterogeneous variances
- Toeplitz
- autoregressive
- compound symmetry without heterogeneous variances

The first covariance structure that converges will be used. The Kenward-Roger approximation will be used to estimate denominator degrees of freedom.

For both primary analysis approaches, LY900014 will be declared noninferior to insulin lispro if the upper limit of the 2-sided 95% CI for the LS mean difference in the change from baseline in HbA1c for LY900014 minus insulin lispro is below +0.4%.

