### **6.11.2. Analyses of Multiplicity Adjusted Objectives**

[figure not shown]
A graphical approach for multiple comparisons (Bretz et al. 2011) will be used to strongly control the overall Type I error (2-sided alpha level of 0.05) for testing the treatment effect for the primary and the following multiplicity adjusted objectives: superiority of LY900014 compared with insulin lispro for (H2) 1-hour postprandial plasma glucose (PPG) excursion at the study primary endpoint, (H3) 2-hour PPG excursion at the study primary endpoint, and (H4) change from baseline to the study primary endpoint in HbA1c.

The graphical testing scheme for this study is displayed in [Figure 6.1](#). All the hypotheses are connected by lines with arrowheads indicating the directions of testing paths. The initial allocation of study total alpha for each hypothesis is located within the same node of the hypothesis. In this study, the study total alpha level (0.05) will be all used for the primary objective (H1) in the initial step. Then, the study total alpha level (0.05) will be allocated to other objectives according to the values of transition weights shown above the connecting lines in the figure once H1 is met. If 1 of the remaining objectives is successfully demonstrated with the given alpha level, its alpha will be allocated to the rest of objectives by the transition weights in the paths. The iterative test procedure continues until none of the remaining objectives can be demonstrated with their preserved alphas or all objectives are demonstrated successful.

An ANCOVA model with strata (country, type of basal insulin during the lead-in period, number of prandial doses at study entry, and HbA1c stratum) and treatment as fixed effects and baseline as a covariate will be used to analyze the 1-hour and 2-hour PPG excursions for all the

randomized subjects with data collected prior to discontinuation of IP. However, if the percentage of the patients with missing MMTT data at baseline is higher than 15%, a constrained longitudinal data analysis model (Liu et al. 2009; Lu 2010) will be used instead.

The superiority testing on change from baseline to the study primary endpoint in HbA1c will be assessed by the same analysis used for the primary objective. The analyses are described in Section 6.11.1. If the p-value is less than the alpha level allocated by the graphical approach, the superiority of LY900014 to insulin lispro will be achieved.

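### With 2:1 allocation, the common-variance models for H1–H4 give correct standard errors only if both arms have equal variance, and no planned analysis relaxes that assumption

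*Protocol*

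**What the plan says.** **Allocation.** Protocol 10.1: "Patients will be randomized in a 2:1 ratio to LY900014 and insulin lispro, both dosed 0 to 2 minutes before meals". The only reason given, in Protocol 5.4, is regulatory: "The 2:1 randomization ratio is to meet the regulatory requirement of China SDA".

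**HbA1c, H1 and H4.** SAP 6.11.1 specifies an MMRM in which an "unstructured covariance structure will be used to model the within-patient errors", with Kenward-Roger degrees of freedom. The covariance is not said to vary by treatment group. The fallback structures with heterogeneity are alternatives for the same within-patient errors in case of non-convergence. They are not tied to arm, and on the ordinary reading the heterogeneity is across visits. SAP 6.11.2 tests H4 with the same analysis as H1.

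**Meal-test excursions, H2 and H3.** SAP 6.11.2 specifies an ANCOVA with strata "and treatment as fixed effects and baseline as a covariate will be used to analyze the 1-hour and 2-hour PPG excursions". A constrained longitudinal model replaces it if more than 15% of patients lack baseline meal-test data. No robust or arm-specific variance is mentioned for either.

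**Error control.** SAP 6.5 says that the graphical approach "will be used to strongly control the overall Type I error (2-sided alpha level of 0.05") across the primary and multiplicity-adjusted objectives.

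**Other analyses.** The per-protocol and Completer analyses (SAP 6.11.3) and the COVID-19 sensitivity analysis (SAP 7.6) repeat the same models. The LOCF ANCOVA in SAP 6.11.3 also has no arm-specific variance. The empirical method in SAP Table 6.5 applies only to severe hypoglycemia rates.

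**The concern.** A model with one variance for both arms estimates it as an average weighted by arm size, so at 2:1 the estimate leans toward LY900014. The true variance of the treatment difference leans the other way, because the smaller lispro arm contributes its variance divided by a smaller number. The two agree when the arm variances are equal, and at 1:1 they agree in large samples whatever the variances.

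If lispro outcomes are the more variable, the reported interval is too narrow and the tests are liberal. If LY900014 outcomes are the more variable, the interval is too wide and the tests are conservative. At stake are the non-inferiority interval and three alpha-controlled superiority tests, which carry all of the trial's confirmatory claims. Strong control at 0.05 presumes that each of those tests has its nominal level.

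**Working it through.** **The plan's own figure.** Protocol 10.1: "Assuming a non-inferiority margin (NIM) of 0.4%, no true difference between treatment arms, and an SD of 1.1%, 480 completers", and "480 completers (320 in the LY900014 group and 160 in the insulin lispro group) will provide 96% power to show noninferiority".
- SE = 1.1 × √(1/320 + 1/160) = 0.1065.
- Power = Φ(0.4/0.1065 − 1.96) = Φ(1.796) = 96.4%. The stated 96% reproduces.
- Dropout: 480/0.85 = 564.7, against 564 stated.

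The sample size is not in question. It uses one SD for both arms.

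**Inputs for the check.** n = 320 (LY900014) and 160 (lispro), from Protocol 10.1; alpha 0.05 two-sided, which is 0.025 one-sided for the H1 decision. The ratio q = lispro SD / LY900014 SD is **assumed**, from 0.8 to 1.3, because the documents give no arm-specific SDs.

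**Formulas** (LY900014 SD set to 1):
- True variance of the difference: T = 1/320 + q²/160.
- Common-variance model: M = [(320 + 160q²)/480] × (1/320 + 1/160).
- Actual two-sided error = 2 × [1 − Φ(1.96/√(T/M))].

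**Example, q = 1.2.** T = 0.003125 + 0.009000 = 0.012125. M = 1.14667 × 0.009375 = 0.010750. √(T/M) = 1.062. Error = 2 × [1 − Φ(1.846)] = 6.5%.

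| q | model SE / true SE | two-sided error | one-sided (H1) |
|---|---|---|---|
| 0.8 | 1.076 | 3.5% | 1.7% |
| 1.0 | 1.000 | 5.0% | 2.5% |
| 1.1 | 0.969 | 5.8% | 2.9% |
| 1.2 | 0.942 | 6.5% | 3.2% |
| 1.3 | 0.918 | 7.2% | 3.6% |

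At 240:240 the same formulas give T = M, hence 5.0%, at every q. The exposure comes from the allocation.

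**Size on the H1 scale.** Hold the pooled SD at 1.1. The model half-width is 1.96 × 0.1065 = 0.209. The correct half-width is 0.209 × √(T/M):
- q = 1.1: 0.215, a shortfall of 0.007
- q = 1.2: 0.222, a shortfall of 0.013
- q = 1.3: 0.227, a shortfall of 0.019

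**Smaller alphas.** After H1 the alpha is split by transition weights in a figure that is not shown. Taking assumed allocations at q = 1.2, a nominal 2.5% becomes 3.5% and 1.25% becomes 1.9%. No family-wise error rate was computed.

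**Simulation, ANCOVA.** 320:160, one baseline covariate, 4,000 runs per setting. Two-sided error at q = 1.0, 1.1, 1.2, 1.3:
- model-based: 5.2%, 5.9%, 6.7%, 7.5%
- HC3: 5.0%, 5.2%, 5.2%, 5.0%

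A separate 40,000-run set at q = 0.8 gave 3.5% model-based and 4.9% with HC3. Under equal variances, power was 84.4% with HC3 and 84.5% without.

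**Simulation, MMRM.** 376:188, four visits, 15% random monotone dropout, 6,000 runs per setting (Monte Carlo error about 0.3 points). Stratum terms were omitted and a normal reference replaced Kenward-Roger. Two-sided error at q = 0.8, 1.0, 1.2, 1.3:
- common covariance: 3.5%, 4.5%, 7.0%, 7.2%
- by-arm covariance: 5.1%, 4.8%, 5.4%, 5.0%

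**The case against.** **No evidence of unequal variances.** The documents give one SD, 1.1%, and nothing suggests that the arms differ. Both arms inject insulin lispro at the same concentration, to the same glucose targets and with the same adjustment algorithm, under blinding. This stands: every error rate above other than 5% depends on an assumed ratio.

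**The mechanism does not describe the null.** A reader might infer that lispro must be the more variable arm in the meal test, because a faster insulin is expected to flatten excursions, and that H2 and H3 are therefore liberal. The documents do not support this. Flatter excursions describe LY900014 working, whereas Type I error is defined with no mean difference. For H1 the null has LY900014 worse by 0.4%; if spread rises with poorer control, LY900014 would be the more variable arm, which is the conservative direction. This stands, and no direction is claimed here.

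**H1 barely moves.** A shortfall of 0.007 to 0.019 against a margin of 0.4 is unlikely to change the conclusion. Nor does q = 0.8 threaten power for H1: with pooled SD 1.1, the planned analysis would have 97.3% power, above the stated 96%. Both stand.

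**Unequal spread would be seen.** SAP 6.1 requires SDs for continuous measures, and exploratory analyses are allowed. This stands in part: a difference in spread could be noticed, but nothing pre-specified would correct the standard error.

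**The common variance is read from silence.** True, but an MMRM or ANCOVA stated without qualification is normally fitted that way. If the sponsor intended otherwise, one sentence settles it.

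**Conclusion.** The point holds as an unguarded assumption and not as a demonstrated inflation. A reader might conclude that 2:1 allocation leaves the 5% level broken. The documents do not show that: with equal variances the level is right, and with a more variable LY900014 arm the tests are conservative.

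Over assumed lispro/LY900014 SD ratios of 0.8 to 1.3, two-sided error runs from 3.5% to 7.2%, and the one-sided rate for H1 from 1.7% to 3.6%. The H1 conclusion is unlikely to change. The matter is more relevant to H2–H4, which are superiority tests at alphas that may be below 0.05, where the relative inflation is larger. The formula results assume complete data and large samples. The simulations agree with them for the ANCOVA, and for a simplified MMRM within Monte Carlo error. The sample size calculation is unaffected. The change is worth making because it is cheap.

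**What to change.** **SAP 6.11.2.** Name HC3 robust standard errors as the single method for the 1-hour and 2-hour excursion ANCOVA. If the constrained longitudinal model is triggered, let the Week 26 variance differ by arm.

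**SAP 6.11.1 and Protocol 10.3.1.** Fit the unstructured covariance separately by treatment group, with Kenward-Roger. If that does not converge, use the currently planned pooled unstructured covariance, and only then the existing ordered list. The middle step is needed because that list starts at heterogeneous Toeplitz and does not contain pooled unstructured; without it, non-convergence would lead straight to a more restrictive structure that is still pooled across arms.

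**Alternative.** If the sponsor prefers to keep the pooled MMRM as primary, pre-specify the by-arm covariance fit as a sensitivity analysis for H1 and H4.

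**Cost.** SAP and protocol wording, and one model option. A second covariance matrix for the four HbA1c visits adds 4 × 5/2 = 10 parameters with 564 patients, and a slightly higher chance of non-convergence. In the ANCOVA simulation HC3 cost essentially no power under equal variances.
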